3. To be performed at the central laboratory. Hematology includes: WBC, differential, platelet count, hemoglobin, and hematocrit. Blood chemistry includes: electrolytes (sodium, potassium, and chloride), glucose, total protein, total bilirubin, ALT, AST, ALP, BUN, and serum creatinine.
4. Subjects who require post-operative rFVIIIIFc treatment for a bleeding episode at home will record their assessment of response to treatment in the eDiary; this assessment is to be made approximately 8 to 12 hours from the time the rFVIIIIFc injection was given to treat the bleeding episode and prior to any additional doses of rFVIIIIFc given for the same bleeding episode.
5. The Investigator/Surgeon will record the assessment of the subject's response to treatment during surgery using a 4-point scale. This assessment will be done within 24 hours after surgery. See [Appendix C](#) and [Appendix E](#).
6. FVIII activity levels should be measured prior to the pre-operative (loading) dose of rFVIIIIFc, and at 30 ± 5 minutes post-dosing. A repeat sample will be taken approximately 6 to 9 hours after this dose, but may alternatively follow the local standard of care for determination of subsequent rFVIIIIFc dosing. During the subject's hospitalization, FVIII activity will be measured daily at the local laboratory, and a plasma aliquot will be prepared for each blood sample drawn for subsequent analysis at the central laboratory.
7. Inhibitor and anti-rFVIIIIFc antibody testing to be performed 2 to 4 weeks prior to surgery, pre-operatively on the day of surgery, 1-2 weeks after surgery, and at the last post-operative visit (for minor surgery, testing is not performed at the last 2 timepoints). For FVIII inhibitor and antibody testing, a wash out of at least 48 hours is recommended.
8. Visit 3 (1-2 Weeks Post Surgery) and Visit 4 (Last Post-Operative Visit) are not performed for subjects who undergo minor surgery. For major surgery, Visit 4 occurs when the subject returns to a regular rFVIIIIFc regimen as determined by the Investigator, and is not required if the return to a regular rFVIIIIFc regimen occurs at Visit 3.

CONFIDENTIAL

The information contained herein may not be used, disclosed, or published without the written consent of Biogen Idec MA Inc.

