5.3.3. Surgery and Rehabilitation

If a subject requires emergent or elective surgery while participating in this study, he may be treated with the dose and regimen of rFVIII Fc deemed appropriate for the type of surgery. All major surgeries will be reported as SAEs.

All major surgical procedures must take place in a center that can provide study treatment, trained study personnel, post-operative assessments, and hematological consultation by the Investigator or Co-Investigator. If the surgery does not occur in such a setting, the subject will be withdrawn from the study. See Section 10.1.3 for provisions when a subject requires major surgery.

CONFIDENTIAL

The information contained herein may not be used, disclosed, or published without the written consent of Biogen Idec MA Inc.

If surgery-related dosing is continued during post-operative rehabilitation and/or physical therapy, the dose of rFVIII Fc will be adjusted to achieve a FVIII trough at a sufficient level to maintain hemostasis.

Subjects will return to a regular rFVIII Fc regimen once all dosing for the post-operative rehabilitation period has been completed. For subjects undergoing major surgery, a visit is required 1-2 weeks after surgery (Visit 3, not required for minor surgery). Visit 4 (Last Post-Operative Visit, not required for minor surgery) occurs when the subject returns to a regular rFVIII Fc regimen as determined by the Investigator, and is required only if the subject did not return to a regular rFVIII Fc regimen at Visit 3.

The surgical period will begin with the subject's first dose of rFVIII Fc given for the surgery (i.e., the pre-surgery dose). This is the pre-operative period of the surgery. The intra-operative period is defined as the time the surgery begins to the time the surgery completes. The post-operative care period is defined as the time period following the completion of the surgery through the last dose of rFVIII Fc given for the surgery, as judged by the Investigator/Surgeon, including doses given to prevent bleeding during the post-operative rehabilitation period.

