16.4.2. General Methods of Analysis

All efficacy endpoints are secondary. No imputation will be applied to any missing efficacy data. For subjects who need/select to have surgeries during the study, their efficacy data during surgical period (including rehabilitation period) will be analyzed separately. The efficacy and surgical/rehabilitation periods will be defined in the statistical analysis plan for the purpose of determining the study periods during which data will be used for select efficacy analyses. Data on bleeding and rFVIIIIFc consumption will be based on the efficacy period; surgical evaluations will be based on the surgical/rehabilitation period.

Analysis of efficacy endpoints that are visit-based will include data from all study visits, whether or not in the efficacy period, unless a visit is coincidental with a surgical/rehabilitation period for a major surgery, in which case it would be excluded.

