- 1 minute before the first prophylactic dose on or after the last date among the dates for discharge from the hospital, post-operative visit 1, post-operative visit 2, the end of rehabilitation.
- If all of the dates mentioned above are missing, then select the first prophylactic dose after the date/time for the end of surgery. If the surgery time was not recorded or recorded as 00:00, then select the surgery date and impute 23:59 for the time. If the end date of the surgery is missing, then select the start date of the surgery and impute 23:59 for the time.
- If there are no prophylaxis doses following the latter of the 6 dates mentioned above, then select the latter of the dates and impute 23:59 for the time if otherwise there is no time associated with the given date (e.g., the subject completed the surgical/rehabilitation period but received no further prophylactic doses).
- If the overall end of study is declared while the subject is still in the surgical/rehabilitation period, then select the date of the end of study and impute 23:59 for the time.

If the treatment regimen after the surgical/rehabilitation period is the episodic regimen, then the end of the surgical/rehabilitation period is

- Imputed as 23:59 on the last date among the dates for discharge from the hospital, post-operative visit 1, post-operative visit 2, and the end of rehabilitation
- If all of the dates mentioned above are missing, then select the date of the end of surgery and impute 23:59 for the time. If the end date of the surgery is missing, then select the start date of the surgery and impute 23:59 for the time.

Two exceptions are noted:

- If 2 (or more) major surgeries are performed without an intervening discharge from the hospital, then the first surgical/rehabilitation period will end 1 minute before the start of the next surgery and the second surgical/rehabilitation period will end as described above.
- If minor surgery is performed during postoperative care or rehabilitation then the surgical/rehabilitation period for the minor surgery will start and end on the day of the minor surgery, at 00:01 and 23:59, respectively, if times are not otherwise provided or recorded as 00:00. The surgical/rehabilitation period for the major surgery will include the minor surgery (ie, the surgical/rehabilitation period for the major surgery does not stop and restart around the minor surgery) and will end as otherwise defined.

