Within the total surgical/rehabilitation period, the time is divided into:

- Intraoperative period: from the date/time of the pre-surgery rFVIIIIFc dose to the date/time of the end of surgery
- Postoperative care period: from the date and time plus 1 minute following the end of surgery to the last dose of rFVIIIIFc given for the surgery, including doses given to prevent bleeding during the postoperative period

- Postoperative rehabilitation period: from the date following the last day of postoperative care to the end of the surgical period as described above

The surgical/rehabilitation period will be determined in the same manner for both major and minor surgeries.

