6.5.4. Consumption

The total annualized rFVIII Fc consumption (IU/kg) will be calculated for each subject using the following formula:

$$\text{Annualized consumption} = \frac{\text{Total IU/kg of study drug received during the efficacy period}}{\text{Total number of days during the efficacy period}} \times 365.25$$

The total amount of rFVIII Fc received will be the sum of the nominal IU/kg administered for each injection based on the units of rFVIII Fc as recorded from the subject's diary and eCRF and his most recent weight.

Total annualized rFVIII Fc consumption will be determined for each treatment regimen during the efficacy period (i.e., excluding surgery/rehabilitation periods [major and minor surgeries]).

For personalized prophylaxis regimen, additional injections administered will be included in the consumption calculations.

Consumption is a secondary endpoint in this study. A description of how consumption will be summarized is provided in Section 7.3.3.

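### For the episodic regimen, SAP 5.3.3 can close the surgical period before the last surgical dose, so later surgical doses count in annualized consumption

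*SAP*

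**What the plan says.** **End rule.** For a subject on the episodic regimen after surgery, SAP 5.3.3 ends the period at 23:59 on the latest of four dates: hospital discharge, post-operative visits 1 and 2, and end of rehabilitation. If all four are missing, "then select the date of the end of surgery and impute 23:59 for the time". If the surgery end date is also missing, the start date is used.

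**Sub-periods.** The same section then divides the total period. One part is postoperative care, which runs to the last dose "given for the surgery, including doses given to prevent bleeding during the postoperative period". The section closes by applying the same method to major and minor surgery.

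**Protocol.** Protocol 5.3.3 starts the surgical period at the first dose given for the surgery and describes post-operative care as "the time period following the completion of the surgery through the last dose of rFVIII Fc given for the surgery". Protocol 16.4.2 leaves the analysis definition to the SAP: "The efficacy and surgical/rehabilitation periods will be defined in the statistical analysis plan".

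**Visits.** The footnotes to the protocol's surgery visit schedule state: "Visit 3 (1-2 Weeks Post Surgery) and Visit 4 (Last Post-Operative Visit) are not performed for subjects who undergo minor surgery".

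**Use of the period.** SAP 5.3.2 adjusts the efficacy period for major and minor surgical periods and restarts it for episodic subjects at 00:01 on the following day. SAP 6.5.4 sums all study drug in the efficacy period, "excluding surgery/rehabilitation periods [major and minor surgeries". SAP 7.1 excludes the same periods from bleeding and consumption analyses.

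**The concern.** The part can outlast the whole. If a subject on the episodic regimen has a minor procedure with none of the four dates recorded, and receives a further dose for that surgery on a later day, the sub-period definition puts that dose inside the surgical period and the end rule puts it outside. The postoperative rehabilitation sub-period, defined to begin after postoperative care, would then start after the total period had closed.

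The end rule is what drives the derivation, so the dose would be counted as episodic consumption. That contradicts the stated intention to remove minor-surgery time. A treated bleed in the same window would enter the episodic ABR. For prophylaxis with the same dates missing, the period runs to the first prophylactic dose after surgery, so intervening surgical doses stay inside it. Efficacy is reported by regimen.

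**Working it through.** No stated figure in the plan depends on this rule, so there is nothing to reproduce. The check is a trace of the rule, followed by an illustration on assumed inputs.

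**Trace.** Take minor outpatient surgery on day 0, the episodic regimen, none of the four dates recorded, and surgical doses on days 0 to k with k at least 1.

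1. By the SAP's sub-period definition, and by Protocol 5.3.3, surgical time lasts to the dose on day k.
2. By the SAP's end rule, the period closes at 23:59 on day 0.
3. By SAP 5.3.2, episodic efficacy time restarts at 00:01 on day 1.
4. By the SAP 6.5.4 formula, which has no exclusion by injection reason, the doses on days 1 to k enter consumption.
5. By the SAP 7.1.1 formula, a treated bleed on days 1 to k enters ABR. Protocol 10.1.3 has unexpected bleeding after surgery recorded, but not bleeding caused directly by surgery.

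If k = 0 there is no discrepancy.

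**Illustration (all inputs assumed).** One dose of d = 50 IU/kg on each of k = 3 days after surgery; other consumption of 1000 IU/kg per year, accruing outside those days; y years of episodic time.

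- Efficacy days under the SAP: T = 365.25y − 1
- Efficacy days if the period ends on the day of the last surgical dose: T_f = T − k
- Other consumption: B = (1000/365.25) × T_f
- SAP result: (B + kd)/T × 365.25
- Reconciled result: B/T_f × 365.25 = 1000

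For y = 1: T = 364.25, T_f = 361.25, B = 989.05. The SAP result is (989.05 + 150)/364.25 × 365.25 = 1142.2, an excess of 142.2 IU/kg per year, or 14.2%.

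For y = 4: T = 1460, T_f = 1457, B = 3989.05. The SAP result is (3989.05 + 150)/1460 × 365.25 = 1035.5, an excess of 35.5, or about 4%.

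**Range** for 1 to 3 daily doses of 20 to 65 IU/kg, and for one captured bleed against an assumed ABR of 30 otherwise:

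| Episodic time | Excess consumption (IU/kg per year) | Excess ABR per captured bleed |
|---|---|---|
| 0.5 year | 34.7 to 375.6 | 1.5 to 1.9 |
| 1 year | 17.3 to 187.3 | 0.8 to 0.9 |
| 4 years | 4.3 to 46.7 | about 0.2 |

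These are effects on one subject's value, not on a group summary.

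**The case against.** **The SAP has authority to define the period.** A reader might infer that the SAP breaches the protocol. It does not: Protocol 16.4.2 hands the definition to the SAP, and Protocol 5.3.3 describes surgical care within the dose rationale. This stands. What remains is the conflict within SAP 5.3.3, which delegation does not cure.

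**Closing on the day of surgery may be a deliberate convention.** The SAP gives a minor procedure performed during recovery from a major one a single-day period, and its planned minor-surgery dosing listing covers only the procedure and that day. That reading is plausible, but in the first case the major-surgery period still covers the later doses. Neither point removes the statement that postoperative care, for minor surgery too, lies within the total period and runs to the last surgical dose.

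**The trigger is narrow.** It is tempting to say that every outpatient minor surgery falls into the fallback. The documents do not show this. The SAP plans a listing of hospitalization data for minor surgery, and continued surgical dosing may come with an end-of-rehabilitation date. The case also needs surgical doses after day 0. This stands.

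**ABR is mostly untouched.** A reader might infer that post-procedure bleeds in general leak into ABR. They do not. A bleed after the last surgical dose belongs to efficacy time under either definition, and bleeding caused directly by surgery is not reported. This stands.

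**The error does not flatter the product.** It raises consumption and, at most, ABR. True, but the result would still not be what the SAP says it reports.

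**Conclusion.** The inconsistency is real and confined to the episodic end rule of SAP 5.3.3. Where all four dates are missing and surgical dosing continues past the day of surgery, those doses enter episodic annualized consumption against the SAP's stated exclusion. ABR is affected only by a treated bleed between day 1 and the last surgical dose.

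The overall effect cannot be sized, because the documents give neither the number of such surgeries nor the doses that follow them. The illustrative overstatement for one subject, about 14% at 1 year and 4% at 4 years, rests wholly on the assumed doses and background consumption, and it shrinks as follow-up lengthens. Both endpoints are secondary and descriptive with no hypothesis test, and inhibitor development is unaffected. The point is worth correcting before the analysis is run, but it does not threaten the study's main conclusion.

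**What to change.** In the episodic part of the SAP 5.3.3 end rule, end the period at 23:59 on the later of:

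- the latest of the four listed dates, or the surgery end date if all four are missing; and
- the date of the last injection labelled for a surgical reason that corresponds to that surgery.

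The section already uses surgical-reason labels to set the start of the period and already sets aside labelled doses that match no surgery, so the same logic can be reused. This brings the end rule into line with the SAP's own sub-periods and with Protocol 5.3.3. The prophylaxis rule can stay as it is.

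The cost is one sentence of SAP text and a small change to the derivation, with no new data collection. The downside is that the end date then depends on the accuracy of injection-reason labels, and SAP Section 9 shows that diary injection reasons were among the fields changed by query.

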5.3.4. Safety Period

The safety period is defined as the period from 8HA01EXT Study Day 1 to the last recorded date. The end of the safety period will be imputed as 23:59 for the time on the last recorded date in the analysis database. The last recorded date is either the date of the last study visit, last telephone call, or the date of the last dose, whichever comes last.

5.4. Electronic Patient Diary (EPD) Data

From approximately 25 Apr of 2016, EPD data cannot be queried for changes which require subject confirmation. However a subset of data issues needing changes which do not require subject confirmation may be handled programmatically. One such issue falls under the heading of Single Vial Consolidation (SVC) and occurs when a dose consists of an injection which uses more than one vial and these vials are erroneously recorded in the EPD as separate injections, albeit within a short time window. As a scenario where these are actually 2 separate doses within a short space of time is medically implausible, these vials can be consolidated into a single record for the dose. The programming algorithm can be summarized as follows

- Identify all injection records within 60 minutes of one another (fields for identification are subject ID and injection date/time)
- Exclude all examples of true duplicates, based upon records with a selected number of key fields identical (fields for identification are subject ID, injection date/time, nominal dose, and lot numbers)
- For the remaining pairs of records:
Exclude them if the reasons for injections are different from each other with the following three types of scenarios: 1) bleed and prophylaxis/additional/OTHER, 2) surgery and prophylaxis/additional/OTHER, and 3) one with the reason that is not provided. Otherwise,
 - Record with earliest injection date/time retained with corresponding contextual information
 - Combine/sum field values related to the dose (e.g. lot numbers, number of vials, volume injected, nominal and actual dose) into the single retained record

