7.1.1. Bleeding Episodes

Bleeding episodes will be recorded in both the EPD and eCRF; this information will be used to derive the secondary efficacy endpoints. During the course of the study the investigator was given the opportunity to disagree with the type of bleed (spontaneous, traumatic) as classified by the subject/caregiver and the subject/caregiver was subsequently given the opportunity to agree or disagree with the reclassification. If the subject/caregiver agreed with the Investigator's assessment, then all analyses subset by type of bleed will be based on the Investigator's determination of the bleed type whether or not the change was made to the subject's records.

A standardized definition of a bleeding episode has been applied to this study, as follows. A bleeding episode starts from the first sign of a bleed, and ends no more than 72 hours after the last treatment for the bleed, within which any symptoms of bleeding at the same location, or injections less than or equal to 72 hours apart, are considered the same bleed. Any injection to treat the bleed taken more than 72 hours after the preceding one will be considered the first injection to treat a new bleed. For the purpose of analysis, the latter injection will be associated with a new bleeding episode and classified as type=Unknown. The location(s) associated with the original bleeding episode will be carried forth to the new bleeding episode; the onset date and time of bleeding will be unknown and hence considered missing. Any bleeding at a different location is considered a separate bleeding episode regardless of the time from the last injection.

This algorithm will also apply when a follow-up injection was recorded subsequent to a prophylactic injection. If the follow-up injection was administered >72 hours after the previous injection to treat a bleeding episode (type=spontaneous, traumatic, follow-up), then the follow-up injection will be classified as a new bleeding episode as described above.

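### SAP 5.4 merges bleed-treatment records within 60 minutes without checking bleed location, so a bleed at a second location can be lost, contrary to SAP 7.1.1

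*SAP*

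**What the plan says.** SAP 5.4 sets out a programmed convention for vials of one dose that the subject logged as separate injections. It works in four steps.

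- Selection: "Identify all injection records within 60 minutes of one another (fields for identification are subject ID and injection date/time"). Bleed location and type are not selection fields.
- Duplicates: "Exclude all examples of true duplicates, based upon records with a selected number of key fields identical".
- Exemption by reason: "Exclude them if the reasons for injections are different from each other with the following three types of scenarios: 1) bleed and prophylaxis/additional/OTHER". The other two exempt scenarios are surgery against the same group of reasons, and a pair in which one reason is missing. Bleed against bleed is not exempt.
- Result: "Record with earliest injection date/time retained with corresponding contextual information", and "Combine/sum field values related to the dose (e.g. lot numbers, number of vials, volume injected, nominal and actual dose) into the single retained record".

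The stated justification is "As a scenario where these are actually 2 separate doses within a short space of time is medically implausible".

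SAP 7.1.1 defines the bleeding episode. Injections at the same location no more than 72 hours apart belong to one bleed. For other locations, "Any bleeding at a different location is considered a separate bleeding episode regardless of the time from the last injection". A sub-location absent from the first report also counts as different, while a later report naming only part of the first report's locations does not. An episode in several locations is one event in overall ABR, but it counts once in each location category reported. Only episodes treated with at least one FVIII dose are counted.

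**The concern.** The justification in 5.4 is about doses. It supports adding the vials together, but it does not settle whether one bleed or two were treated, because one dose can treat two simultaneous bleeds. The rule nevertheless discards the later record's bleed information along with its separate identity as an injection. Where that record names another location, 5.4 and 7.1.1 give different answers for the same data.

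The outputs that depend on the answer are overall ABR and ABR by location and type (SAP 7.3.1), the secondary endpoint of spontaneous joint bleeds (SAP 2.2.2), the response percentages that use all bleeding episodes as denominator (SAP 7.3.5), and injections and dose per bleed (SAP 7.4.1). Annualized consumption is not affected, since the units sum to the same total.

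There is also a tension inside the SAP. Section 5.4 reserves programmed handling for changes that need no subject confirmation, yet the change-code table in Section 9 lists a change of bleed location as needing it. Dropping the later location has a similar effect on the analysed data.

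**Working it through.** The plan gives no count or effect size for this rule, so there is no figure to reproduce. The check applies both sections to the same pairs of records.

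**Inputs.** 60-minute window, exemptions and retention rule: SAP 5.4. Episode definition (location and the 72-hour limit; type is not a criterion), treated-bleed rule and ABR formula: SAP 7.1.1. Maximum participation of 4 years: SAP 3.1. Shorter follow-up times below are assumptions.

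**Step 1: does a bleed/bleed pair merge?** Yes. After duplicates are set aside it meets none of the three exemptions.

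**Step 2: episodes counted, second record 30 minutes after the first.**

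| Later record | 7.1.1 without the merge | After the 5.4 merge |
|---|---|---|
| Same location, same type | 1 | 1 |
| Same location, different type | 1 | 1 |
| Location already part of the first record | 1 | 1 |
| Different joint | 2 | 1 |
| Different location category | 2 | 1 |
| Different location and different type | 2 | 1 |
| Different joint, which has a further injection at 48 hours | 2 | 2 |

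The loss occurs only when the location differs. It is recovered when the second site later receives its own injection outside the window.

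**Step 3: size per lost episode, if the records are separate bleeds.** ABR = episodes / days × 365.25, so one lost episode lowers that subject's ABR by 365.25 / days.

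- 0.5 year (assumed): 365.25 / 182.625 = 2.00
- 1 year (assumed): 365.25 / 365.25 = 1.00
- 2 years (assumed): 365.25 / 730.5 = 0.50
- 4 years (maximum): 365.25 / 1461 = 0.25

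For illustration, 8 bleeds in 4 years give an ABR of 8/4 = 2.00. One lost episode gives 7/4 = 1.75.

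**Step 4: size if the pair is one multi-location bleed.** Overall ABR is 1 event either way. Two joints also count once in the joint category, so nothing changes there. If the categories differ, for example joint and muscle, 7.1.1 requires a count in each, and the merge leaves only the first record's category. The second category loses 365.25 / days.

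**Step 5: same location, different type.** The count is 1 either way. Only the label changes: the merged record carries the first record's type, which can move an episode between the spontaneous and traumatic summaries.

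**The case against.** The strongest reply is that the convention targets one dose whose vials were logged separately. If a subject tagged those vials with two sites, the truth may be one multi-location bleed, and leaving the records unmerged would over-count overall ABR. This stands as a limit on the overall-ABR claim. It does not rescue the rule, because 7.1.1 would still require the second location category to be counted. One diary report can also carry several locations, so split entry is not the only way to record simultaneous bleeds, and affected pairs may be rare.

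Section 5.4 describes its algorithm as a summary, so the program may contain a location check. If so, one sentence in the SAP closes the point. As written, the steps yield a result contrary to 7.1.1.

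A reader might infer that the rule can only remove bleeds and so biases ABR in one direction. The documents do not support that. The merge keeps the earliest injection time, and 7.1.1 opens a new episode of unknown type after more than 72 hours. Take same-location records at 0:00 and 0:50 and a follow-up at 72:30. Unmerged, the last gap is 71:40 and there is one bleed. Merged, it is 72:30 and there are two.

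A reader might also infer that bleeds of another type are erased contrary to the bleed definition. They are not, because type does not separate episodes in 7.1.1.

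Finally, the impact assessment in SAP Section 9 uses the same convention, so comparing it with the main analysis would not isolate this loss. That is not a defect of the assessment, which addresses queried diary changes and unsupported manual records. The regulator's 2014 agreement, as reported there, concerns subject confirmation for this class of change and does not mention location.

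**Conclusion.** The conflict is real and confined to location. For non-duplicate bleed/bleed pairs within 60 minutes whose later record names a new location or sub-location, SAP 5.4 drops what SAP 7.1.1 says must be counted, unless a later injection for that site restores it. If the records are separate bleeds, one episode is lost from overall ABR, worth 0.25 at 4 years or 1.00 at an assumed 1 year for that subject. If they are one multi-location bleed, only location-specific ABR is wrong, and only where the categories differ. For same-location pairs of different type, the count is right and only the label is fixed arbitrarily.

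These are per-subject figures. The documents do not give the number of affected pairs, so no group effect can be computed and it may be small. A percentage such as 1/9 = 11% for someone with 9 bleeds describes one assumed subject and should not be read as the trial-level effect. All analyses are descriptive, so no test result is at stake. The conclusion rests on reading the 5.4 steps as complete.

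**What to change.** In SAP 5.4, add a condition for pairs in which both reasons are treatment of a bleed: consolidate only when the later record's location and sub-location are the same as, or contained in, those of the first record. Otherwise leave the pair unmerged and apply 7.1.1. Each record should keep its own vials and dose, so that both episodes meet the requirement of at least one FVIII dose. Moving all the dose to the first record while keeping the second as an episode would not meet it.

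State which type label applies when merged records differ in type. Report the number of pairs with differing location or type, so that readers can judge the possible over-count if some unmerged pairs were one multi-location bleed.

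The cost is one matching condition, two or three sentences in the SAP and one count from the diary data. For unmerged pairs, the injections-per-bleed and dose-per-bleed tables will show two episodes, each with its own part of the dose. The documents do not say whether the program is final; if it is, the affected outputs would need a re-run.
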